5.2 Exclusion Criteria

5.2.1 Patients who have had chemotherapy or radiotherapy within 4 weeks prior to entering the study or those who have not recovered from adverse events due to agents administered more than 4 weeks earlier.

Note: Subjects with \leq grade 2 neuropathy are an exception to this criterion and may qualify for the study

Note: If subject received major surgery, they must have recovered adequately from the toxicity and/or complications from the intervention prior to starting therapy

- 5.2.2** Metformin use in the last 3 months
- 5.2.3** Patients who are receiving any other investigational agents.
- 5.2.4** Has known active central nervous system (CNS) metastases and/or carcinomatous meningitis; subjects with previously treated brain metastases may participate provided they are stable (without evidence of progression by imaging for at least four weeks prior to the first dose of trial treatment and any neurologic symptoms have returned to baseline), have no evidence of new or enlarging brain metastases, and are not using steroids for at least 7 days prior to trial treatment; this exception does not include carcinomatous meningitis which is excluded regardless of clinical stability.
- 5.2.5** History of allergic reactions attributed to compounds of similar chemical or biologic composition to *Nivolumab and Metformin*.
- 5.2.6** Has a known history of active tuberculosis (TB) (*Bacillus tuberculosis*)
- 5.2.7** Has a diagnosis of immunodeficiency or is receiving systemic steroid therapy or any other form of immunosuppressive therapy within 7 days prior to the first dose of trial treatment
- 5.2.8** Has active autoimmune disease that has required systemic treatment in the past 2 years (i.e. with use of disease modifying agents, corticosteroids or immunosuppressive drugs); replacement therapy (e.g., thyroxine, insulin, or physiologic corticosteroid replacement therapy for adrenal or pituitary insufficiency, etc.) is not considered a form of systemic treatment.
- 5.2.9** Has known history of, or any evidence of active, non-infectious pneumonitis.
- 5.2.10** Has an active infection requiring systemic therapy.
- 5.2.11** Has known substance abuse disorders that would interfere with cooperation with the requirements of the trial.
- 5.2.12** Has received prior therapy with an anti-programmed death (PD)-1, anti-PD-L1, or anti-PD-L2 agent.
- 5.2.13** Has a known history of human immunodeficiency virus (HIV) (HIV 1/2 antibodies).
- 5.2.14** Has known active hepatitis B (e.g., hepatitis surface antigen [HBsAg] reactive) or hepatitis C (e.g., hepatitis C virus [HCV] ribonucleic acid [RNA] [qualitative] is detected).
- 5.2.15** Has received a live vaccine within 30 days of planned start of study therapy.
Note: Seasonal influenza vaccines for injection are generally inactivated flu vaccines and are allowed; however intranasal influenza vaccines (e.g., Flu-Mist) are live attenuated vaccines, and are not allowed

5.2.16 Uncontrolled intercurrent illness including, but not limited to, ongoing or active infection, symptomatic congestive heart failure, unstable angina pectoris or myocardial infarction within 6 months of study entry, serious cardiac arrhythmia requiring medications, baseline corrected QT (QTc) >450 msec or previous history of QT prolongation while taking other medications.

5.2.17 Other medications, or severe acute/chronic medical or psychiatric condition, or laboratory abnormality that may increase the risk associated with study participation or study drug administration, or may interfere with the interpretation of study results, and in the judgment of the investigator would make the subject inappropriate for entry into this study

5.2.18 Has a known additional malignancy that is progressing or requires active treatment; exceptions include basal cell carcinoma of the skin or squamous cell carcinoma of the skin that has undergone potentially curative therapy or in situ cervical cancer. Subjects with prior malignancies are eligible if the subject has been disease free for >5 years.

5.2.19 Is pregnant or breastfeeding, or expecting to conceive or father children within the projected duration of the trial, starting with the screening visit through 120 days after the last dose of trial treatment.

5.3 Screen Failures

Minimal data for subjects who fail screening will be collected such as demographic information and the reason for screen failure. Such subjects may be re-screened at the discretion of the investigator after approval by the Data and Safety Monitoring Committee (DSMC). The reason for the need to re-screen a subject will be documented in the subject's source documents.

6. TREATMENT PLAN

6.1.1 Agent Administration

Treatment will be administered on an outpatient basis. Reported adverse events and potential risks are described in Section 7. Appropriate dose modifications are described in Section 6. No investigational or commercial agents or therapies other than those described below may be administered with the intent to treat the patient's malignancy.

Table 1: Cycle 1 only (Day -14 through 28) Lead-in period

| Regimen Description | | | | | |
|----------------------------|-------------------------------------|-------------|--------------|-----------------|---------------------|
| Agent | Premedications ; Precautions | Dose | Route | Schedule | Cycle Length |
| | | | | | 42 days |

| | | | | | |
|------------|----------------|-----------------------------------|----|------------------------------------|--|
| Metformin | Take with food | 500 mg tablet am, 500 mg pm | PO | Twice daily D-14 through -12 | |
| Metformin | Take with food | 500 mg tablet am, 1000 mg pm | PO | Twice daily D -11 through -8 | |
| Metformin | Take with food | 1000 mg tablet am, 1000 mg pm | PO | Twice daily D -7 through -1 | |
| Metformin* | Take with food | 1000 mg tablet and, 1000 mg pm | PO | Twice daily, D1-28 | |

*If subject cannot tolerate 1000 mg po twice daily, will resume the highest tolerated dose of Metformin.

NOTE: The patient will be requested to maintain a medication diary of each dose of medication (Metformin). The medication diary ([Appendix B](#)) will be returned to clinic staff at the end of each course. Patients with diabetes mellitus will be requested to keep a blood glucose log for the first 4 weeks of the trial ([Appendix C](#))

Table 2: Cycle 2 and subsequent cycles (28 days)

| Regimen Description | | | | | |
|---------------------|------------------------------|------|-------|----------|--------------|
| Agent | Premedications ; Precautions | Dose | Route | Schedule | Cycle Length |

| | | | | | |
|------------|--|--------------------------------|--------------------|--------------------|-------------------|
| Nivolumab | Premedicate with Acetaminophen 650 mg po once prior to Nivolumab, optional | 480 mg | IV over 30 minutes | Day 1 | 28 days (4 weeks) |
| Metformin* | Take with food | 1000 mg tablet and, 1000 mg pm | PO | Twice daily, D1-28 | |

* If subject cannot tolerate 1000 mg po twice daily during Cycle 1, subject will continue the maximum tolerated dose of Metformin as in cycle 1 for the subsequent cycles.

NOTE: The patient will be requested to maintain a medication diary of each dose of medication (Metformin). The medication diary (Appendix B) will be returned to clinic staff at the end of each course.

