1. STUDY SYNOPSIS

| |
|---|
| 
Title of Study: Phase II trial of Nivolumab and Metformin in patients with treatment refractory MSS metastatic Colorectal Cancer
 |
| 
Study Centers: Emory University Winship Cancer Institute
 |
| 
Study Phase: Phase II
 |
| 
Objectives:
 
Primary Objective:
 
▪ The primary endpoint of this study is to Evaluate the effect of metformin in combination with nivolumab on the overall response rate (ORR) (Primary Objective) as assessed by RECIST.1.1 
Secondary Objectives:
 
▪ To determine the effect of the metformin and nivolumab combination on clinical (PFS, OS) outcomes and biochemical (CEA) response.▪ To compare the effect metformin and nivolumab combination on immune and metabolic biomarkers in the tumor microenvironment and systemic circulation (pre and post treatment paired biopsies required). |
| 
Trial Design/Methodology: Single arm phase II study. 28 patients with previously treated (previously treated with fluoropyrimidine, oxaliplatin, irinotecan and EGFR inhibitor – if RAS wildtype) metastatic CRC will be started on metformin and nivolumab combination.
 
Treatment
 
1. Patients will start taking metformin 500 mg po BID for 3 days, then 500 mg am and 1000 mg pm for 4 days, then 1000 mg po bid for 1 week. Patients of the study will get paired biopsies as outlined in study calendar.2. If a patient cannot tolerate metformin 1000 mg po BID the patient will resume the metformin dose which was tolerable3. After 2 weeks of metformin only therapy (lead-in period) patients will start nivolumab 480 mg IV q4 weeks and continue metformin 1000 mg PO BID (or the tolerated dose of Metformin).4. Restaging scans will be performed at the end of cycle 2, then every 8 weeks for 2 years.5. Correlative assays will include- immune profiling of TILs and circulating lymphocytes, plasma cytokine levels and metabolic biomarkers. These will be performed at baseline at baseline, cycle 1 day 1, cycle 1 day 15, Cycle 3 Day 1 and at progression 
Treatment regimen and trial diagram:
 |

Main criteria for exclusion:

- MSI status
- Autoimmune conditions that may require systemic steroids or other immunosuppressive treatments
- Pregnancy or breast feeding

Investigational product and administration:

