6.12 Subject Replacement Strategy

Patients who do not complete the intended course of therapy due to reasons other than toxicity, clinical or radiographic disease progression will be considered as in-evaluable for the primary endpoint and will be replaced. Subject are not able to tolerate metformin despite 2 dose reductions in the first 2 weeks of the trial (Metformin only phase) will be considered inevaluable and replaced.

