7. STUDY CALENDAR

Winship Protocol #: Winship4494-18
Protocol: Nivolumab + Metformin
Protocol/Amendment No.: Version 6/June 13, 2023
Study Flow Chart

36

| Trial Period: | | Treatment Cycles ^a | | | | | | | | | | End of Treatment | Post-Treatment | | |
|---|----------------|--------------------------------|-----|----------------|------|-----|-----|-----|-----|-----|-----|-------------------|---------------------|-------------------------------|--------------------|
| | | Main Study Screening (Visit 2) | | 1 ^a | 2 | 3 | 4 | 5 | 6 | 7 | 8 | | | | |
| Treatment Cycle/Title: | Day | D-14 | D-7 | D1 | D15 | | | | | | | Discon | Safety Follow-up | Follow Up Visits ^b | Survival Follow-Up |
| Scheduling Window (Days): | -28 to -1 | | | ± 3 | ± 3* | ± 3 | ± 3 | ± 3 | ± 3 | ± 3 | ± 3 | At time of Discon | 30 days post discon | Every 8 weeks post discon | Every 12 weeks |
| Informed Consent | X | | | | | | | | | | | | | | |
| Inclusion/Exclusion Criteria | X | | | | | | | | | | | | | | |
| Demographics and Medical History | X | | | | | | | | | | | | | | |
| Prior and Concomitant Medication Review | X | X | X | X | X | X | X | X | X | X | X | X | X | X | |
| Metformin Administration ^c | | X | X | X | X | X | X | X | X | X | X | | | | |
| Drug Diary and Pill Count (Metformin) section 13.5 ^c | | X | | X | X | X | X | X | X | X | X | X | | | |
| Blood glucose log for diabetic patients | | X | X | X | X | | | | | | | | | | |
| Nivolumab administration ^c | | | | X | | X | X | X | X | X | X | | | | |
| Post-study anticancer therapy status | | | | | | | | | | | | | X | X | |
| Survival Status | | | | | | | | | | | | | X | X | X |
| Review Adverse Events | | | X | X | X | X | X | X | X | X | X | X | X | X | |
| Full Physical Examination | X | X | | X | | X | X | X | X | X | X | | | | |
| Directed Physical Examination | | | | | X | | | | | | | | X | X | X |
| Vital Signs and Weight | X | X | | X | X | X | X | X | X | X | X | X | X | X | |
| ECOG Performance Status ^d | X ^d | X | | X | X | X | X | X | X | X | X | X | X | X | |
| Pregnancy Test – Urine or Serum β-HCG | X ^j | | | | | | | | | | | | | | |
| PT/INR and aPTT | X | | | | | | | | | | | | | | |
| CBC with Differential | X | X ^e | | X | X | X | X | X | X | X | X | X | X | X | |
| Comprehensive Serum Chemistry Panel | X | X ^e | | X | X | X | X | X | X | X | X | X | X | X | |
| Fasting triglyceride, cholesterol and glucose | X | | | | | X | | | X | | | | | | |
| CEA | | X | | X | X | | X | | X | | X | | | | |

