| Urinalysis | X | | | | | X | | | X | | | X | | | |
| T3, FT4 and TSH | X | | | | X | | | X | | | X | X | X | X | |
| ECG | X | | | | | | | | | | | | | | |

| Trial Period: | Main Study Screening (Visit 2) | Treatment Cycles ^a | | | | | | | | | | End of Treatment | Post-Treatment | | |
|---|--------------------------------|-------------------------------|-----|----------------|----------------|----------------|----------------|----------------|---------|----------------|--------------------------------|---------------------|---------------------------|-------------------------------|--------------------|
| | | 1 ^a | | 2 | 3 | 4 | 5 | 6 | 7 | 8 | To be repeated beyond 8 cycles | | Safety Follow-up | Follow Up Visits ^b | Survival Follow-Up |
| Treatment Cycle/Title: | 1 ^a | D-14 | D-7 | D1 | D15 | | | | | | | Discon | | | |
| Day | | | | | | | | | | | | | | | |
| Scheduling Window (Days): | -28 to -1 | | | ± 3 | $\pm 3^*$ | ± 3 | ± 3 | ± 3 | ± 3 | ± 3 | At time of Discon | 30 days post discon | Every 8 weeks post discon | Every 12 weeks | |
| Tumor Imaging | X | | | | | X ^g | | X ^g | | X ^g | | | | | |
| Newly Obtained Tissue Collection ^h | X | | | X ^h | X ^h | | | | | | | | | | |
| Correlative Studies Blood Collection ⁱ | X | | | X ⁱ | X ⁱ | | X ⁱ | | | | | X ⁱ | | | |

- a. Each cycle is 4 weeks, and there is 14 days lead in period in cycle 1
- b. Only for patients with ongoing treatment related toxicities
- c. Metformin will be taken 500 mg po BID for D-14 to-12, 500 mg am and 1000 mg pm for D-11 to 8, 1000 mg am and 1000 mg pm for D- 7 to -1, and continued 1000 mg BID for the rest of the study (if not able to tolerate 1000 mg BID during D1-14 period subject will be on maximum tolerated dose). Study coordinator will call the patient on Day -13 to confirm the subject is taking the right dose of medication. Nivolumab will be given after biopsy#2 (same day or up to 5 days later), and then repeated every 4 weeks.
- d. ECOG performance status should be done within 14 days or less from day 1 of cycle 1
- e. Lab results from screening may be used if completed within 1 week of day -1
- f. Baseline imaging within 4 weeks of day 1 is acceptable
- g. Scans will be done at the end of cycle 2 (± 3 days), then repeated every 2 cycles (q 8 weeks)

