8.1.5.4 Cycle 1 Day -7 phone call

- Metformin
- Review of adverse events, dosing compliance and concomitant medication (by clinical trial coordinator via phone call)

8.1.5.5 Cycle 1 Day 1

- Record concomitant medications
- Vitals (temperature, HR, BP and RR)
- History and physical exam, pill diary and pill count, blood glucose log for diabetic patients
- ECOG performance status
- Toxicity assessment
- Laboratory Assessments
 - Hematology hemoglobin, hematocrit, red blood cell count, white blood cell count with differential and platelet count
 - Chemistry sodium, potassium, chloride, bicarbonate, magnesium, calcium, phosphorus, blood urea nitrogen, creatinine, glucose (random), total bilirubin, LDH, total protein, ALP, ALT, AST, and albumin
- Blood sample 20 cc for correlative work
- **Subject# 1-9, 19-23** (14 patients in total) will get biopsy#2 of paired biopsy (same day or up to 5 days later)
- Continue metformin
- Nivolumab will be started after biopsy#2 (same day or up to 5 days later).
- Nivolumab 480 mg will be administered as a 30-minute IV infusion in the infusion center. Given the variability of infusion pumps, a window of -5 minutes and +10 minutes is permitted (i.e., infusion time is 30 minutes: -5 min/+10 min).

8.1.5.6 Cycle 1 Day 15

- Record concomitant medications
- Vitals (temperature, HR, BP and RR)
- History and physical exam, pill diary and pill count, blood glucose log for diabetic patients
- ECOG performance status

- Toxicity assessment
- Laboratory Assessments
 - Hematology hemoglobin, hematocrit, red blood cell count, white blood cell count with differential and platelet count
 - Chemistry sodium, potassium, chloride, bicarbonate, magnesium, calcium, phosphorus, blood urea nitrogen, creatinine, glucose (random), total bilirubin, LDH, total protein, ALP, ALT, AST, and albumin
 - Tumor marker – CEA
- Blood sample 20 cc for correlative work
- The second half of the patients **Subject #10-18, 24-28** (14 patients in total) will get biopsy#2 of paired biopsy (same day or up to 5 days later)
- Continue metformin

8.1.5.7 Cycle 2 Day 1

- Record concomitant medications
- Vitals (temperature, HR, BP and RR)
- History and physical exam, pill diary and pill count
- ECOG performance status
- Toxicity assessment
- Laboratory Assessments
 - Hematology hemoglobin, hematocrit, red blood cell count, white blood cell count with differential and platelet count

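### As extracted, the Section 6.1.1 dosing tables give no nivolumab in cycle 1 and call all of Day -14 to 28 the lead-in; the rest of the protocol starts nivolumab in cycle 1 after 14 days of metformin

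*Combined protocol and SAP*

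**What the plan says.** **The treatment plan.** Section 6.1.1 has two dosing tables. Table 1 is titled "Cycle 1 only (Day -14 through 28) Lead-in period". Its four agent rows are all metformin: three titration steps from Day -14 to Day -1, then one row for Day 1 to 28. The only nivolumab row is in the second table, headed "Table 2: Cycle 2 and subsequent cycles (28 days" (the bracket closes after the last word), where it is given on Day 1.

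**The rest of the protocol.**
- Section 1 (synopsis): "After 2 weeks of metformin only therapy (lead-in period) patients will start nivolumab 480 mg IV q4 weeks".
- Section 6.12 describes the metformin-only phase as falling "in the first 2 weeks of the trial (Metformin only phase".
- Section 7 (calendar): the row "Nivolumab administration" is marked at cycle 1 Day 1, blank at Day -14, Day -7 and Day 15, and marked again from cycle 2. Footnote a reads "Each cycle is 4 weeks, and there is 14 days lead in period in cycle 1".
- Section 8.1.5.5 (Cycle 1 Day 1 visit): "Nivolumab 480 mg will be administered as a 30-minute IV infusion in the infusion center".
- Appendix B: the lead-in pill diary runs from Day -14 to Day -1.

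**Nivolumab and the second biopsy.** Calendar footnote c and Section 8.1.5.5 place nivolumab after biopsy 2 without naming a cohort in that statement. Footnote h attaches the same instruction to the subjects biopsied at Cycle 1 Day 1 (1-9 and 19-23). Subjects 10-18 and 24-28 have biopsy 2 at Cycle 1 Day 15.

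**The concern.** Section 6 is the treatment plan, and the protocol does not say whether it or the Section 7 calendar prevails when they differ. A pharmacy or site working from Tables 1 and 2 as printed would give 28 more days of metformin alone before nivolumab than one working from the calendar.

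Two parts of the study depend on this timing. The primary endpoint is response rate, and by calendar footnote g "Scans will be done at the end of cycle 2", so the start day sets how much nivolumab a patient has had at the first response assessment. The second secondary objective (Section 3.2) and Section 4.4 use paired biopsies to study the combination. If nivolumab starts only in cycle 2, both biopsies precede it, and the pair can show only the effect of metformin.

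**Working it through.** The question is one of schedule, so the check is a day count. Days are nominal, with no Day 0.

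**1. Reproduce the plan's own figure.** Table 1 gives a cycle 1 length of 42 days.
- Lead-in titration: 3 + 4 + 7 = 14 days (Day -14 to -1).
- Day 1 to 28: 28 days.
- 14 + 28 = 42.

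The 42 days is a correct cycle length and agrees with footnote a. It is not part of the conflict. The conflict lies in the lead-in label, which covers 42 days in Table 1 and 14 days elsewhere (42 − 14 = 28 days apart), and in the absence of a nivolumab row.

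**2. Key days.** Cycle 2 Day 1 = 28 + 1 = Day 29. End of cycle 2 = 2 × 28 = Day 56. Biopsy 2 is at Day 1 for subjects 1-9 and 19-23 (9 + 5 = 14) and at Day 15 for subjects 10-18 and 24-28 (9 + 5 = 14).

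**3. Compare the two schedules.**

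| | Tables 1-2 as printed | Calendar with footnote h |
|---|---|---|
| First nivolumab | Day 29 | Day 1 |
| Metformin alone before it | 42 days | 14 days |
| Nivolumab doses before the end-of-cycle-2 scan | 1 (Day 29) | 2 (Days 1 and 29) |
| Second biopsies after any nivolumab | 0 of 28 | 14 of 28 |

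For the last row: under the tables, Day 1 and Day 15 both precede Day 29, even with the permitted 5-day biopsy delay (15 + 5 = Day 20). Under the calendar, the Day 1 cohort is biopsied before its first dose and the Day 15 cohort after it, so 14 of 28 qualify.

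**4. What depends on the PDF.** In the machine-read text Table 1 arrives in two blocks, and the first ends in a row that is blank except for the cycle length. A row may have been lost.
- If the PDF has no cycle 1 nivolumab row, the whole comparison in step 3 stands.
- If it has one, the step 3 differences fall away and only the label on Day -14 to 28 conflicts with the 14-day lead-in stated elsewhere.

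**5. Footnote c.** Read alone, it would have subjects 10-18 and 24-28 wait for their Day 15 biopsy before starting nivolumab. Against that reading, the calendar leaves Day 15 blank for nivolumab, footnote h ties the instruction to the Day 1 cohort, and the Day 15 visit list (Section 8.1.5.6) names the biopsy and continued metformin but no nivolumab.

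**The case against.** The strongest objection is that the central fact may come from a damaged table, and a broken table is not an error in the plan. The trial diagram, which might settle the matter, is also not shown. This stands as a limit on certainty about the missing row. It does not reach the Table 1 title, which is intact.

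The title can be defended as meaning the cycle that contains the lead-in, which is how footnote a puts it, and the table rows do separate Day -14 to -1 from Day 1 to 28. That reading is possible, but the title does not say it, and a metformin-only Day 1 to 28 row beneath it suggests the opposite.

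It can also be said that the protocol largely resolves itself. Every visit-level passage puts nivolumab in cycle 1, Section 8.1 says the flow chart summarizes what is done at each visit, and Section 8.1.5 sends the reader to Section 7 for visit requirements. This lowers the practical risk considerably. It still falls short of a rule for what to do when the treatment plan disagrees.

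Three stronger readings are tempting but not supported:
- *A third start time, after the Day 15 biopsy, for half the patients.* Only footnote c in isolation supports this; the three passages in step 5 point to Day 1. It is an ambiguity to clear up, not a rival schedule of equal weight.
- *A range of days from first dose to scan, built from the biopsy and scan windows.* The calendar also has a ±3-day visit window, and the protocol does not say whether the scan day moves when dosing shifts, so such ranges would rest on unstated assumptions.
- *A distorted primary analysis through the 80% compliance rule in Section 8.1.1.6.* The prescribed number of nivolumab doses in the first two cycles would differ, but the rule works on a percentage of what is prescribed, and no consequence for the analysis follows from the documents.

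**Conclusion.** The inconsistency is real and should be corrected. Tables 1 and 2 as printed and the remaining passages differ by one 28-day cycle in the first nivolumab dose (Day 29 against Day 1). The difference is one dose against two before the first response scan, and 0 against 14 of 28 second biopsies taken after nivolumab. These figures assume nominal days and no cycle 1 nivolumab row in Table 1 of the PDF. If that row exists, the point reduces to the lead-in label.

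A reader might infer that the response rate is biased or the trial's power reduced. The documents give no basis for computing any such effect, and the agreement among the other passages makes it likely that sites follow the calendar. Confidence is medium because of the state of Table 1. The footnote c ambiguity is secondary.

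**What to change.** 1. Check Table 1 against the PDF for a cycle 1 nivolumab row.
2. Reconcile the titles and rows of Tables 1 and 2 with the synopsis, Section 6.12, the calendar and its footnotes a, c and h, Sections 8.1.5.5 and 8.1.5.6, and Appendix B, so that all give one first-nivolumab day and one lead-in length.
3. State in footnote c and Section 8.1.5.5 which biopsy cohort the after-biopsy-2 instruction covers, and make this agree with footnote h.

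Which start day is right is for the sponsor to decide. The cost is protocol wording only: a table title or row, and one sentence each in footnote c and Section 8.1.5.5. The sample size, endpoints and planned analyses are not changed.
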